5.1 DEMOGRAPHIC DATA

Variables	Honey group (n = 43)	Control group (n = 43)	p value
Age (years)			
Sex			
Male, n (%)			
Female, n (%)			
Race			
Malay, n (%)			
Chinese, n (%)			
Indian, n (%)			
Others, n (%)			
BCVA (Log MAR)			
Duration of JOAG (years)			
Number of topical antiglaucoma medications			
Received surgical intervention for IOP control			

5.2 COMPARISON OF MEAN SERUM LEVEL OF IL-6 PRE AND POST 3 MONTHS OF HONEY (KELULUT) TREATMENT AMONG PATIENTS WITH JOAG

Comparison of mean serum level of IL-6 pre and post 3 months of honey (Kelulut) treatment among patients with JOAG

Mean serum IL-6 level value	Group	Mean diff (95% CI)	p
Time			
Baseline	Honey No honey		
3 months' post treatment	Honey No honey		

5.3 COMPARISON OF MEAN RETINAL NERVE FIBER LAYER THICKNESS PRE AND POST 3 MONTHS OF HONEY (KELULUT) TREATMENT AMONG PATIENTS WITH JOAG

RNFL thickness	Group	Mean diff (95% CI)	p value
Time			
Baseline	Honey No honey		
3 months' post treatment	Honey No honey		

5.4 COMPARISON OF DRY EYE DISEASE PARAMETERS PRE AND POST 3 MONTHS OF HONEY (KELULUT) TREATMENT AMONG PATIENTS WITH JOAG

[figure not shown]
Comparison of TBUT	Group	Mean diff (95% CI)	p value
<hr/>			
Time			
Baseline	Honey No honey		
3 months' post treatment	Honey No honey		

Comparison of Schirmer test	Group	Mean diff (95% CI)	p value
<hr/>			
Time			
Baseline	Honey No honey		
3 months' post treatment	Honey No honey		

5.5 COMPARISON OF LEVEL OF GLYCATED HEMOGLOBIN PRE AND POST 3 MONTHS OF HONEY (KELULUT) TREATMENT AMONG PATIENTS WITH JOAG

HbA1c	Group	Mean diff (95% CI)	p value
<hr/>			
Time			
Baseline	Honey No honey		
3 months' post treatment	Honey No honey		

CHAPTER 6: FLOW CHART

CHAPTER 7: GANTT CHART

Year	2024	2024-2025		2025-2026		2026
Months	Jan-May	Jun-Nov	Dec-May	Jun-Nov	Dec-May	Jun
Proposal preparation and ethical approval			→			
Data collection					→	
Data analysis/interpretation					→	
Report writing					→	
Submission of research book						→

CHAPTER 8: MILESTONE

Data	Expected achievement
Jan 2024 – November 2024	Proposal presentation (Department of Ophthalmology USM) Jawatankuasa Etika Penyelidikan Manusia (JEPEM) USM presentation NMRR application
December 2024-February 2025	JEPEM and NMRR approval
March 2025 – May 2025	30% of data collection
June 2025 – November 2025	80% of data collection 30% of report writing
December 2025 – May 2026	100% data collection 100% of data analysis 100% of report writing
June 2026	Submission of research book

CHAPTER 9: ETHICAL CONSIDERATION

9.1. ETHICS

This study will be conducted after the approval from the Ethical Committee USM, in accordance to the Declaration of Helsinki and International Conference of Harmonisation (ICH). All researchers of this study were GCP-certified.

9.2. VULNERABILITY

The subjects for this study involve subjects with JOAG attending the Ophthalmology Clinic HUSM, HRPZ II, HSNZ and HSIP that fulfills the study requirement and capable of giving their own consent. Legal age in Malaysia is 18 years old.

For participant aged 15 to-under 18 years old: Co-sign informed consent with parents are obtained.

They will be provided full information about the study's purpose, duration, procedure, benefit, risk and institutional approval. They will be given full authority to decide and full freedom to participate in the study without affecting his/her condition management and care. The investigator could withdraw the subject, or the subject could withdraw from participation in the study any time without penalty or any loss of benefits. The reason for withdrawal will be recorded. In cases of developing allergic reaction or severe adverse effects, appropriate treatment will be provided accordingly and patients will be followed up in ophthalmology clinic for further management and treatment.

9.3. CONFLICT OF INTEREST

There is no conflict of interest in any parts of this study, including towards the medical devices and pharmaceutical companies.

9.4. INFORMED CONSENT

Patients will be briefed regarding the study design, any adverse reactions related to the procedures and the anticipated benefits of the study. A summary of this information will be presented in written consent form. Consent is obtained from patients or guardians who agrees to participate in the study. A copy of this will be given to the subjects. A list of contact number of the investigators will also be included in the patient information leaflet. Any further information regarding the study will be informed to patient throughout the study period and patients will be informed regarding the result at the end of the study.

All the subjects will be informed regarding the study findings. This information will be shared as part of the informed consent process, ensuring participants are well-informed about the scientific basis for the study and any relevant outcomes from similar studies, including those that suggest potential benefits for retinal health. This ensures transparency and gives participants a comprehensive understanding of the context of the study.

9.5. PATIENT WITHDRAWAL

The investigators could withdraw the subject, or the subject could withdraw their participation from the study without any penalty or loss of benefits. The reason for withdrawal would be recorded in the Case Report form. Reasons for cessation of study subjects by investigators includes non-compliance with protocol and study requirement and adverse effect towards the drug.

9.6. RISK AND BENEFITS TO STUDY PARTICIPANTS

There are no serious adverse effects by the study procedures such as slit lamp examination/ RNFL measurement/venipuncture for serum IL 6 measurement. Dosage of the honey provided to the patient is within the therapeutic dosage. Patient will be periodically for adverse effect during monthly follow up. In case of developing adverse effects to the honey, patients are advised to immediately stop the honey, contact the study doctor and seek immediate treatment from the emergency service at the nearest hospital.

9.7. DATA HANDLING AND RECORD KEEPING

Participants' medical records will be kept in the study site (Ophthalmology Clinic and Visual Sciences, School of Medical Hospital Universiti Sains Malaysia. Data obtained from the study will be kept by the principal investigator in a password locked computer for up to 3 years after the study has ended after which the study data will be subsequently destroyed. No future research will be done using the similar data or biospecimens.

9.8. PRIVATE AND CONFIDENTIALITY

All participants will be given a subject identification number to maintain privacy and confidentiality. Participants will be informed of their clinical findings and will be managed accordingly during the study. Medical information will be kept confidential unless disclosed by law, the researcher, the ethical board for this study and regulatory authorities for the purpose of verifying clinical trial procedures and/or data. Data collection forms are anonymous and the data will be entered into SPSS software. Only the research team members have access to the data. In the event that this study is published, study result will be published in a collective data format with no identification

of any individual or disclosure of the participants' personal information. If the study being published, relevant permissions will be obtained prior to publication.

9.9. COMMUNITY SENSITIVITIES AND BENEFITS

There is no element of sensitivity to the community in this research study. The findings from this study will greatly improve future management of JOAG both from the local and global community.

9.10. INCENTIVES AND HONORARIUM

All participants will be given a leaflet/ brochure that contains information regarding the juvenile open angle glaucoma and beneficial effects of honey on the neuromodulation involved in the progression of glaucoma disease. This study is fully funded, therefore there is no cost for the participant. Additionally, participants will continue to receive their standard conventional medications for glaucoma or other underlying conditions as prescribed by their treating ophthalmologist or healthcare provider, and these will be provided at their usual cost or as per their existing healthcare arrangements. An honorarium will be provided to participants as a token of appreciation for their involvement in the study. The honorarium will be issued once the MSO (Medical and Scientific Office) grant is approved.

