4.5. SELECTION CRITERIA

Inclusion criteria

All JOAG patients age 15 years old and above – 40 years old at the time of diagnosis

Compliant to conventional treatment and achieved target intraocular pressure

Exclusion criteria

Patients with allergy to honey or honey-based products

OCT signal less than 6/10

Concurrent retinal diseases and other optic neuropathies

Systemic neurodegenerative disease

Systemic comorbidities such as diabetes mellitus and autoimmune diseases

Patients on other honey-based products for the last 3 months

Patient who consumes honey-based products during the study duration of 3 months

(monitoring via honey-diary, return of the used sachet during the follow up visits)

Patients on anti-oxidants, traditional medications or herbal products for the last 3 months

Topical usage of steroids, systemic steroids and non-steroidal anti-inflammatory drugs.

Sepsis

Compliance less than 75%.

The duration of treatment with honey will be 3 months (90 days), patient who missed more than 22 sachets of honey will be excluded.

Compliance will be assessed through regular monitoring via monitoring of honey-diary and patients are required to return the used honey sachets during clinic visits.

Withdrawal criteria

All patients who do not receive standard treatment for JOAG

All candidates who develops sudden unexpected severe allergic reaction (SUSAR) to the investigated product.

Participants who withdraw or drop out of the study will not be replaced. Follow-up assessments will continue for all participants, including those who withdraw from the honey supplementation, to allow for comprehensive data collection and minimize loss to follow-up. Throughout the study period, participants will continue their conventional glaucoma medications without interruption to ensure standard clinical care is maintained.

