4.7. HONEY SUPPLEMENT

The honey used in this study is Brainey Madu Kelulut, harvested from *Heterotrigona Itama*. It will be supplied for a total of three months after the recruitment and completion of initial examination and blood sampling. The participants in the ‘no honey’ group did not receive any placebo. Patient in the ‘no-honey’ group is prohibited from consuming products that is based on honey Kelulut or other honey-based products throughout the study period. The control group will consist of matched JOAG patients receiving standard treatment without honey.

Both the patients and the Principal Investigator will not be blinded by the modality of treatment.

Participants were instructed regarding the consumption of the honey by the Principal Investigator. The honey will be supplied in the form of sachet, dosage of 30g per sachet per day for 3 months. The participants are advised to consume the honey at least 30 minutes prior to meals or other medications to avoid any interactions. Participants are also advised not to mix or dilute the honey using other solutions or food products. Participants are also prohibited from consuming other honey-based products throughout

the duration of the study. Those who develop any allergic reaction such as rashes, shortness of breath, wheezing, dysphagia or anaphylactic reactions are advised to immediately discontinue the product and seek immediate treatment from the nearest Emergency Department and contact the Principal Investigator regarding the side effects.

The principal investigator will also advise the patients regarding the compliance to treatment. The compliance will be monitored via a printed diary that will be given upon enrolment. Patients are required to tick on the diary upon completion of the honey sachets daily.

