12.1 PATIENT INFORMATION AND CONSENT FORM

12.2 DATA COLLECTION FORM

12.3 HONEY TREATMENT DIARY

Serial number	
MRN	
Group	

DATA COLLECTION FORM

Supplementary Kelulut Honey Therapy In Juvenile Open-Angle Glaucoma: Effects On IL-6, RNFL And Dry Eye

A. BIODATA OF PATIENT:

Date of birth	
MRN	
Age	
Gender	
Race	

B. SYSTEMIC DISEASES:

[figure not shown]
[figure not shown]
Diabetes mellitus Type I	
Diabetes mellitus Type II	
Hypertension	
Hypercholesterolemia	
Autoimmune disease	
Malignancy	
Tuberculosis	
Systemic lupus erythematosus	
Allergy	
Others	

C. DIAGNOSIS:

	RIGHT EYE		LEFT EYE	
Type of glaucoma	JOAG	POAG	JOAG	POAG
Date of diagnosis				
Onset of disease				
Duration of disease				
Severity of glaucoma	Mild		Mild	
	Moderate		Moderate	
	Severe		Severe	

[figure not shown]
[figure not shown]
D. OCULAR EXAMINATION**PRE-HONEY**

Date of examination:

	RIGHT EYE		LEFT EYE	
Visual acuity	unaided		unaided	
	pinhole		pinhole	
Intraocular pressure	RE			
	LE			
Gonscopy (Shaffer Grading)				
Fundus				
Humphrey visual field test	Pattern			
	MD			
	VFI			
Antiglaucoma eyedrops				
Types of ocular surgery				

POST HONEY

Date of examination:

	RIGHT EYE		LEFT EYE	
Visual acuity	unaided		unaided	
	pinhole		pinhole	
Intraocular pressure	RE			
	LE			
Gonscopy (Shaffer Grading)				
Fundus				
Humphrey visual field test	Pattern			
	MD			
	VFI			
Antiglaucoma eyedrops				
Types of ocular surgery				

E. Investigated parameters

		PRE-HONEY	POST HONEY
Serum IL-6 level (pg/mL)			
Retinal nerve fiber layer thickness (μm)	Mean		
	Superior		
	Inferior		
	Nasal		
	Temporal		
Tear break up time (seconds)			
Schirmer test (mm)			
Glycated haemoglobin HbA1c(%)			

TREATMENT DIARY

Name	
IC	
RN	

HONEY TREATMENT DIARY (to be completed by patient)

DAY	DATE	HONEY USAGE (✓ FOR YES, X FOR NO)	NOTES (SIDE EFFECTS)
1			
2			
3			
4			
5			
6			
7			
8			
9			
10			
11			
12			
13			
14			
15			
16			
17			
18			
19			
20			
21			
22			
23			
24			
25			
26			
27			
28			
29			
30			
31			
32			
33			
34			
35			
36			
37			
38			

39			
40			
41			
42			
43			
44			
45			
46			
47			
48			
49			
50			
51			
52			
53			
54			
55			
56			
57			
58			
59			
60			
61			
62			
63			
64			
65			
66			
67			
68			
69			
70			
71			
72			
73			
74			
75			
76			
77			
78			
79			
80			
81			
82			
83			
84			
85			
86			
87			
88			
89			
90			

MONTHLY SUMMARY TABLE (to be completed by principal investigator)

MONTH	NUMBER OF SACHET CONSUMED	SIDE EFFECTS	COMPLIANCE (%)

1			
2			
3

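### Open-label controls who are forbidden honey are given a leaflet on honey's benefits, and the named checks on honey use would not reliably detect control contamination

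*Protocol*

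**What the plan says.** **Leaflet.** Protocol 9.10: "All participants will be given a leaflet/ brochure that contains information regarding the juvenile open angle glaucoma and beneficial effects of honey". The sentence makes no exception for the control arm and gives no time of distribution.

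**Controls.** Protocol 4.7 gives them no placebo and says that a control patient "is prohibited from consuming products that is based on honey Kelulut or other honey-based products throughout the study period". On blinding, the same section says: "Both the patients and the Principal Investigator will not be blinded by the modality of treatment".

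**Exclusion and its monitoring.** Protocol 4.5 excludes anyone who takes honey-based products during the 3 study months. The check named there is "monitoring via honey-diary, return of the used sachet during the follow up visits".

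**What those tools record.** Protocol 4.7: "Patients are required to tick on the diary upon completion of the honey sachets daily". The diary in Appendix 12.3 has a daily column headed "HONEY USAGE (✓ FOR YES, X FOR NO", and its monthly summary has a column "NUMBER OF SACHET CONSUMED" beside side effects and percent compliance. Section 4.6 ties the monthly visits to honey supply and compliance with the regimen. Section 4.10.7 judges compliance from the diary and the used packages.

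**Other products.** Protocol 4.5 also excludes "Patients on anti-oxidants, traditional medications or herbal products for the last 3 months". The on-study prohibition in 4.7 names honey products only.

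**The concern.** The objectives in 3.1.2 compare patients with and without honey, so the contrast depends on controls staying off it. These controls know their allocation, have a sight-threatening disease, and live where, by section 2.5, Kelulut honey can be farmed on a large scale. Giving them material on honey's benefits works against the prohibition in 4.7. It also works against one advantage of allocating whole centres (4.6), which is that no study honey is handed out at control centres.

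If some controls take honey, the honey-minus-control differences in IL-6, RNFL thickness, TBUT and Schirmer shrink. A null result could then mean either no effect or a diluted contrast, and the data might not show which. For HbA1c the stated hypothesis is that honey causes no increase, so the same dilution favours the conclusion the study hopes to reach.

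**Working it through.** **1. Does any check reach non-study honey in controls?** The relevant places, side by side:

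| Place in protocol | What it covers | Reaches non-study honey in controls? |
|---|---|---|
| 4.5, returned sachets | Sachets supplied by the study | No. Controls receive none, and a returned sachet cannot reveal purchased honey in either arm |
| 4.5 and 4.7, diary | A daily tick when the sachet is finished | Only if controls are given it and read it more widely than 4.7 describes |
| 4.6, monthly visits | Compliance with the honey regimen, and side effects | Not stated |
| 4.10.7, 3-month visit | Diary and used packages | As for the diary and the sachets |
| 9.11, parental role | Use of the study product, entered in the diary | Not stated |
| Appendix 12.2, data form | Outcomes and eye examination | No field |
| Appendix 12.3, diary form | Yes/no honey use; monthly sachet count | No field for source or type of honey |

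The exclusion in 4.5 is worded for both arms, but the tools attached to it are described as measures of compliance with the supplied product.

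**2. The plan's own sample size.** Section 4.4 gives a calculated size of 24, 80% power, a 5% significance level and 20% attrition. 24 / (1 − 0.20) = 30 per group, which reproduces the stated figure. I therefore read the 24 as per group. The 24 itself cannot be re-derived, because no effect size, SD or correlation is given. The only allowance made is for attrition.

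**3. Illustration of dilution.** Assumptions: two-sided 5% (sidedness is not stated), patient-level analysis, and a share c of controls taking honey with the full effect. The documents give no value for c, so 10% to 30% is my assumed range.

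- Observed difference = (1 − c) × true difference.
- At 80% power the standardised signal is 1.96 + 0.84 = 2.80, so power = Φ(2.80 × (1 − c) − 1.96).
- Evaluable patients per arm needed to restore 80% power = 24 / (1 − c)², rounded up. Dividing by 0.80 adds the attrition allowance.

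| c | Power with 24 per arm | Needed per arm | With 20% attrition |
|---|---|---|---|
| 0 | 80% | 24 | 30 |
| 10% | Φ(0.56) ≈ 71% | 24/0.81 → 30 | 38 |
| 20% | Φ(0.28) ≈ 61% | 24/0.64 → 38 | 48 |
| 30% | Φ(0.00) ≈ 50% | 24/0.49 → 49 | 62 |

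A calculation with the t distribution gives the same powers to the nearest percent.

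**The case against.** The strongest reply has five parts.

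- **Timing and content of the leaflet.** Section 9.10 gives no date, and the item sits under incentives, so it could be handed over at the end. The leaflet itself is not in the documents. A reader might infer that controls certainly receive persuasive material at entry, but the text does not establish that. What stands is that nothing prevents early distribution.
- **Detection.** A reader might infer that contamination would go wholly unseen. The documents do not support that. Section 4.7 has the diary handed over at enrolment without naming an arm, and its yes/no honey column could be completed by a control. What stands is that no section tells controls to complete it or to enter non-study honey, so detection is unreliable but not shown to be absent.
- **Consent.** Section 9.4 already has participants told of similar studies suggesting retinal benefit, so postponing the leaflet leaves some incentive in place. That is correct and limits what the fix can achieve. The leaflet is still a separate item that can be avoided.
- **Size.** Full effect would require controls to match the study intake for 3 months, and occasional use would probably dilute less. Control centres hold no study honey to share. With two centres per arm, the patient-level 80% is itself doubtful. All of this stands, so the powers are illustrations and not forecasts.
- **Antioxidant and herbal products.** A reader might infer that controls are free to start these and so bias the comparison. The documents only leave it unclear whether the entry restriction continues. Similar use in both arms would not by itself produce the shrinkage described.

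**Conclusion.** The point holds in a limited form. The protocol gives material on honey's benefits to unblinded controls who must avoid honey, does not delay it until outcomes are measured, and names monitoring that fits the supplied sachets and not non-study honey. Contamination may be encouraged and would not be reliably detected. The direction of bias is towards no difference, which for HbA1c favours the hypothesis.

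The size is unknown. A fall from 80% to about 71%, 61% or 50% rests on assumed contamination of 10%, 20% or 30% with full effect, and on a patient-level analysis that ignores allocation by centre. The change is worth making because it is cheap and would make a null result easier to interpret.

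**What to change.** 1. **Section 9.10.** Give the disease information during the trial and hold the part on honey's benefits until after the 3-month assessment. Because of the disclosure in 9.4, this reduces the incentive but does not remove it.
2. **Sections 4.5 and 4.7, Appendix 12.3.** State that both arms complete the 90-day diary. Add a column for any non-study honey, antioxidant or herbal product taken that day, and report use by arm.
3. **Analysis.** Keep participants who took non-study honey in the main comparison. This conflicts with the exclusion of on-study honey consumers in 4.5, so the two must be reconciled explicitly.
4. **Sections 4.5 and 4.7.** Reconcile the antioxidant, traditional and herbal restriction, worded for the 3 months before entry, with the on-study prohibition that names honey only, so that it is clear whether the former continues during the study.

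Cost: a reprinted leaflet and a reworded form, a small diary burden for controls, and honey information reaching patients about 3 months later.

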9.11. PARENTAL ROLE

Parents play a pivotal role in monitoring their child's compliance with both the conventional treatment and the investigational product; they also must ensure the child

follows the instructions that must be followed throughout the study period. The consumption of the product should be monitored directly by parents and be recorded in a honey diary provided to the participants, which will be handed to the investigator at the end of the study period.

9.12. ROLE OF PRINCIPAL INVESTIGATOR

Principal investigator will not be the direct service provider of the recruited patients. The principal investigator will be in charge if the subjects may have any enquiries or develop health issues throughout the study.

CHAPTER 10: RESEARCH REGISTRATION

10.1 Registration

Registration number: RSCH ID-24-04301-DXV

Name of trial registry: National Medical Research Register (NMRR)

